**Table 3 Clinical laboratory assessments** 

Sample		Test
Blood	Hematology	hemoglobin, hematocrit, red blood cell count, white blood cell count and differential (neutrophils, lymphocytes, monocytes, eosinophils, basophils), platelet count
	Blood chemistry	alkaline phosphatase, creatinine, ferritin, C-reactive protein, albumin, alanine aminotransferase, amylase, aspartate aminotransferase, gamma glutamyl transpeptidase, total bilirubin, blood urea, fasting blood sugar, lipase, sodium, potassium, calcium
	Thyroid function	triiodothyronine (T3), thyroxine (T4), thyroid stimulating hormone.
	Coagulation function	prothrombin time (PT), activated partial thromboplastin time (APTT), thrombin time (TT)), fibrinogen (FIB).
	Pregnancy test	β-hCG test
Urine	Urinalysis	glucose, bilirubin, ketone, specific gravity, occult blood, pH, protein, urobilinogen, nitrite, and leukocytes. Microscopic urinalysis if warranted by dipstick results, urine sediment will be microscopically examined for the presence of red blood cells, white blood cells, casts, crystals, epithelial cells, and bacteria.

## 9.1.6.4 Safety laboratory testing

Routine safety laboratory testing includes hematology, blood chemistry and urine routines, thyroid function and coagulation function and laboratory testing is outlined in **Table 3**. Each blood sample was

approximately: blood routine 2 ml, blood chemistry 4 ml, ferritin 4 ml, thyroid function 3 ml, coagulation function 2ml.

## 9.1.6.5 Immunogenicity assessment

Serum immunogenicity (humoral immunity / antibody) is detected by ELISA and neutralizing antibody test. Each blood sample for ELISA assessments will be approximately 7.5 mL, and for neutralizing antibody test will be approximately 7.5 mL.

Should a blood sampling be performed during a vaccination visit, this sampling must occur before the vaccination of the investigational vaccine or placebo.

# 9.1.6.6 CMI assessments

## 9.1.7 Safety assessments

During the trial, safety assessments will include collection and recording of local (vaccination site) and systemic reactions (including fever), unsolicited AEs (serious and non-serious). Refer to Section 10.1 for safety definitions. Details on collection and reporting of reactions and AEs are in Section 10.2. Refer to Section 9.3.4 for details about the diary cards distribution, review and collection processes.

## 9.1.8 Contraception guidance

Subjects will be provided with guidelines on acceptable methods of contraception.

Female subject of childbearing potential and sexually active will have to use an "acceptable contraceptive method" from 2 weeks before screening through 2 months after the last dose of trial vaccine, and will be advised not to donate ova during this period.

Male subjects must be advised not to donate sperm during this period.

## 9.1.9 Pregnancy

For WOCBP, pregnancy testing will be performed at Screening Visit, and blood pregnancy testing will be performed before the boost vaccination of investigational vaccine/placebo.

Subjects must have a negative serum  $\beta$ -hCG pregnancy test at screening and before boost vaccination.

For the sake of the safety of a subject, if a female subject or female partner of a male subject is pregnant during the study vaccination, it must be reported to the Fosun with a pregnancy reporting form A within 24 hours after learning the event. At the same time, the pregnant patient must be followed up to determine the pregnancy outcome (provided that the female partner of a male subject agrees to have the data collected), including spontaneous or induced abortion, details of

childbirth, congenital malformations, or maternal or neonatal comorbidities, etc., and a pregnancy reporting form B will be filled for reporting.

Normal deliveries should be followed up at least one year after birth; other pregnancy results must be reported as serious adverse events (SAE), and the SAE form must be completed and reported, in addition to the pregnancy report form. Selective abortion without complications is not considered as an adverse event. If other SAEs occur during pregnancy, the SAE form must also be completed and reported.

If the subject becomes pregnant during the trial, she will not receive any further doses of any investigational vaccine/placebo. Should the pregnancy occur after administration of investigational vaccine/placebo in a blinded condition, the investigator must inform the subject of their right to receive information on the investigational vaccine/placebo injected. If the subject chooses to know unblinded information, the individual blind should be broken by the investigator and procedures must be followed, as described in Section 8.5.

## 9.1.10 Documentation of trial entrance/randomization

Only subjects who have signed an ICF at Screening Visit, meet all of the inclusion criteria and none of the exclusion criteria, are eligible for allocation/randomization into the vaccination phase.

One single subject screening number will be assigned to each subject at Screening Visit. In the study, subjects will be randomized at 1:1:1 with each cohort of 24 subjects to inject BNT162b1 or placebo.

## 9.1.11 Documentation of subjects who are not enrolled/randomized

If a subject who signs the ICF is found to be not eligible within the screening period, the investigator should complete the eCRF and explain the reasons.

The primary reason for un-enrollment/non-randomization is recorded in the eCRF using the following categories:

- Screen failure: does not meet one or more inclusion criteria; does meet one or more exclusion criteria;
- Withdrawal by subject;
- Trial terminated by Fosun Phar.

A subject may be a temporary screen failure under the following circumstances: due to temporary conditions such as receipt of immunosuppressive or immunomodulatory therapies, blood products, immunoglobulins, or vaccines, in the respective prohibited periods (see exclusion criteria), or in the event that a subject has an indeterminate pregnancy test result. Subjects screen failed for the above-mentioned reasons may be rescreened once they cease to meet the respective exclusion criteria. Should the respective repeated test results be available within the prime screening period, no new subject screening numbers will be required; the repeated screening tests will be recorded in the appropriate CRF (unscheduled visit form). Should the respective repeated test results not

be available within the prime screening period, the subject would need to be screen failed and all screening procedures and tests would need to be repeated with a new subject screening number.

Subject screening numbers assigned to subjects who fail screening should not be reused.

#### 9.2 Subject treatment compliance

The investigator records all injections of investigational vaccine/placebo given to the subject in the eCRF.

# 9.3 Schedule of observations and procedures

The schedule for all trial-related procedures for all evaluations is shown in **Table** 2. Assessments should be completed at the designated visit(s)/time point(s).

# 9.3.1 Screening procedures (Screening Visit)

See Section 6.1 for more details about the enrollment.

The following screening procedures will be performed at Screening Visit:

- 1. Confirm informed consent, and complete and collect ICF (see Section 9.1.1). Before performing any other trial procedure, the signed ICF needs to be obtained. Only applicable for newly screened subjects.
- 2. Assign subject ID number (see Section 6.1 for more details about the enrollment).
- 3. Assess eligibility criteria (see Sections 7.1 and 7.2).
- 4. Collect demographics (see Section 9.1.2).
- 5. Collect medical history (including alcohol taken), travel history (to SARS-CoV-2 endemic countries and SARS-CoV-2 endemic regions of China), and prior/concomitant medications/vaccinations (see Section 9.1.2).
- 6. Perform "complete" physical examination (see Section 9.1.4).
- 7. Check vital signs (see Section 9.1.5).
- 8. Perform 12-lead ECG and chest CT test (see Section 9.1.5).
- 9. Collect blood sample for eligibility screening tests (hematology, biochemistry, see Section 9.1.6).
- 10. Collect fingertip blood for SARS-CoV-2 and HIV antibody.
- 11. Collect oropharyngeal swabs for SARS-CoV-2 testing.
- 12. Collect urine sample for eligibility screening urinalysis.
- 13. For WOCBP, serum pregnancy testing will be performed at Screening Visit (see Section 9.1.6 for pregnancy test), and contraception guidance will be provided (see Section 9.1.8 and 9.1.9).

# 9.3.2 Pre-vaccination procedures

The following procedures will be performed at Visit 1 (Day 1) and Visit 5 (Day 22):

- 1. Collect medical history, travel history (to SARS-CoV-2 endemic countries and SARS-CoV-2 endemic regions of China), and concomitant medications/vaccinations (see Section 9.1.2).
- 2. Perform symptom-directed physical examination (if deemed necessary, see Section 9.1.4).
- 3. Assess eligibility criteria (see Sections 7.1 and 7.2) at Visit 1 (Day 1).
- 4. Check vital signs (see Section 9.1.5).
- 5. Randomize subject (only at Visit 1 on Day 1), a random number was obtained (the random number was used as the unique subject ID number) (see Section 9.1.10).
- 6. Collect blood sample for clinical laboratory and immunogenicity assessment (see Section 9.1.6).
- 7. For WOCBP, serum pregnancy testing will be performed before boost vaccination (see Section 9.1.9).

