#### Vaccination protocol and visit schedule

Each randomized subject will be given two doses of either BNT162b1 (10 or 30 μg) or placebo intramuscularly (IM) – one vaccination at Visit 1 (on Day 1) and one vaccination at Visit 5 (on Day 22), into one third of the deltoid muscle, preferably in the non-dominant arm.

From the treatment randomization, each subject will be required to attend 12 clinical visits:

All immunized subjects will attend Visit 1 (prime vaccination) on Day 1, Visit 2 on Day 2 (24 hours after prime vaccination), Visit 3 on Day 8 (7 days after prime vaccination), Visit 4 on Day 15 (14 days after prime vaccination), Visit 5 on Day 22 (boost vaccination), Visit 6 on Day 29 (7 days after boost vaccination), Visit 7 on Day 36 (14 days after boost vaccination), Visit 8 on Day 43 (21 days after boost vaccination), Visit 9 on Day 50 (28 days after boost vaccination), Visit 10 at Month 3, Visit 11 at Month 6 and Visit 12 at Month 12.

Blood samples of subjects in adult group will be collected at the following visits for different tests: at Screening Visit (Visit 0) for eligibility screening tests (including clinical laboratory), at Visits 2, 3, 6 for routine safety laboratory testing (visits 2, 6 coagulation function test, visit 2, 6, 11 thyroid function test), at Visit 1 (prior to prime vaccination) and Visits 5 (prior to boost vaccination), 6, 8, 10, 11, 12 for humoral immunity (antibody). Blood sample will be collected at Visit 1 (prior to prime vaccination) and Visits 6, 8, 11 for cell-mediated immunity (CMI). Urine samples will be collected at Screening Visit (Visit 0) for eligibility screening and collected at Visits 2, 3, 6 for regular safety laboratory testing; serum samples of women of childbearing potential will be collected at Screening Visits (Visit 0) and Visit 5 (prior to boost vaccination) for pregnancy test. Fingertip blood will be collected during the screening visit (visit 0) for detection of SARS-CoV-2 antibody and HIV antibody.

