# 9.1.6 Blood sample and urine sample collection

Blood samples will be collected at each site visit: ie, at Screening Visit for eligibility screening tests (clinical laboratory testing, see Section 9.1.6.3), at Visits 2, 3 and 6 for routine safety laboratory testing (see Section 9.1.6.4 for Visits 2, 6 coagulation function test, Visits 2, 6, 11 thyroid function test). Blood samples for immunogenicity (anti-S1/anti-RBD IgG and SARS-CoV-2 neutralizing antibody) will be collected at Visits 1, 5, 6, 8, 10, 11 and 12 for adults and at Visits 1, 5, 6, 8, 11 and 12 for the elderly (see Section 9.1.6.5).

Should a blood sampling be performed during a vaccination visit, this sampling must occur before the injection of the investigational vaccine or placebo. Serum sample will be collected for women of childbearing potential at Screening Visit and Visit 5 before each investigational vaccine/placebo injection for pregnancy testing (see Section 9.1.9). Figertip blood samples will be collected at Screening Visit for SARS-CoV-2 serostatus determination (see Section 9.1.6.1) and HIV serostatus determination (see Section 9.1.6.2).

Urine samples will be collected for all subjects at Screening Visit for eligibility screening (see Section 9.1.6.3), and at Visits 2, 3 and 6 for routine safety laboratory testing (see Section 9.1.6.4).

All samples will be collected in accordance with acceptable laboratory procedures. Samples of immunogenicity and CMI testing will be processed and stored at the study site as described in the provided Laboratory Manual.

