# 9.3.4 Post-vaccination procedures

The following post-vaccination procedures will be performed at Visit 1 (Day 1) and Visit 5 (Day 22):

- 1. After vaccination, the subject will be observed for at least 6 hours on site, including observation for immediate reactions and body temperature measurement. Vital signs will be performed at 1, 3, and 6 h (±15 min) post each immunization. Information should be recorded in the eCRF as immediate reactions. The investigator or delegate will take the opportunity to remind the subject how to measure solicited reactions and body temperature as part of this observation period. All safety data will be collected in the subject's source documents.
- 2. Provide the subject with a diary card, and train the subject on how to use it.
  - Careful training of the subject on how to record concomitant medications, how to measure solicited reactions and body temperature, how to complete the diary card and how often to complete the diary card. Training should be directed at the individual(s) who will perform the measurements of solicited reactions and those who will enter the information into the diary

card. This individual may or may not be the subject, but if a person other than the subject enters information into the diary card, this person's identity must be documented in the trial file and this person must receive training on the diary card. Training of the subject on how to measure a vaccination site AE should be performed while the subject is under observation after vaccination.

Diary card instructions must include the following: the subject must understand that timely completion of the diary card on a daily basis is a critical component of trial participation. The subject should also be instructed to write clearly and to complete the diary card with sign pen. Any corrections to the diary card that are performed by the person completing the diary card should include a single strikethrough line with a brief explanation for any change and be primeed and dated.

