7.1.2 Definitions and Derivations

Baseline

Unless otherwise specified, baseline is defined as the last available value prior to the prime immunization.

> Conversion among day, month and year

Month = day/30.4375, and year = day/365.25, rounded to a decimal place.

Study Day

Taking the date of first dosing as the start date,

- \checkmark If study date < date of first dosing, then study day = study date date of first dosing
- \checkmark If study date >= date of first dosing, then study day = study date date of first dosing + 1

Adverse Events Times

Occurrence time of AE (day) = AE onset date – the corresponding immunization date.

Duration of AE = end date of AE - AE onset date + 1.

Treatment Emergent Adverse Event (TEAE)

Treatment Emergent Adverse Event (TEAE), which is defined as any AE with an onset after the first immunization (if the AE was absent before the first immunization) or worsened after the first immunization (if the AE was present before the first immunization). The implementation of TEAE complies with the following rules: AE with missing start time or AE occurs after or on the day of the prime immunization will be regarded as TEAE, and otherwise will be regarded as non-TEAE.

> The Severity of related TEAE

If the severity of related TEAE under China NMPA Guidance is at least grade 1, which under FDA Guidance is less than grade 1 (ie. NULL in EDC), the corresponding event will not be regarded as adverse event under FDA Guidance.

Similarly, if the severity of related TEAE under FDA Guidance is at least grade 1, which under China NMPA Guidance is less than grade 1 (ie. NULL in EDC), the corresponding event will not be regarded as adverse event under China NMPA Guidance.

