7.6.3 Vital Signs

Descriptive statistics for each vital sign parameters at each time point and change from baseline will be provided by group.

All of vital sign data will be listed by subject.

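### Section 9.3.2 lists pre-injection laboratory samples that the schedule does not contain, and the SAP does not use the same-day Visit 5 vital signs as a reference for the boost

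*Protocol*

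**What the plan says.** **Schedule.** Section 9.3.2 opens with "The following procedures will be performed at Visit 1 (Day 1) and Visit 5 (Day 22". Item 6 of its list is "Collect blood sample for clinical laboratory and immunogenicity assessment (see Section 9.1.6". Items 3, 5 and 7 are each tied to one visit; item 6 is not. Item 7 is the pregnancy test, so item 6 means something else.

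Section 9.1.6, to which item 6 refers, places the draws "at Visits 2, 3 and 6 for routine safety laboratory testing", after screening. The synopsis agrees for adults, "at Visits 2, 3, 6 for routine safety laboratory testing", and names the same visits for the elderly. Section 9.3 says "The schedule for all trial-related procedures for all evaluations is shown in" Table 2. There, in both age groups, haematology and chemistry are marked at Visit 0, 24 h, Day 8 and Day 29 only.

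**Reference for change.** SAP 7.1.2 states: "Unless otherwise specified, baseline is defined as the last available value prior to the prime immunization". Protocol Section 13.1.2 has the same rule. SAP 7.6.3 adds: "Descriptive statistics for each vital sign parameters at each time point and change from baseline will be provided by group". Section 7.6.2 treats laboratory values likewise and adds shifts from baseline to worst grade. Neither section specifies another baseline. For collection, Section 9.3.4 says "Vital signs will be performed at 1, 3, and 6 h (±15 min) post each immunization". Section 9.3.2 item 4 and the pre-boost column of Table 2 also place a vital-sign reading at Visit 5 before the injection.

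**The concern.** There are two linked problems.

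First, someone working from 9.3.2 would draw blood that Table 2 does not contain. Whether a Day 1 laboratory baseline exists, and whether a value exists just before the boost, depends on which section is followed.

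Second, the SAP refers every laboratory and vital-sign change to one point before the prime dose. A change so defined at 1, 3 or 6 h after the boost mixes the acute effect of the boost with whatever happened over the preceding three weeks. The plan expects the two doses to behave differently. Protocol Section 4.2.4.1 reports that in the US study's 30 µg group fever occurred in 8.3% after dose 1 and 75.0% after dose 2. It also reports lymphocyte falls after dose 1, and grade 2 neutropenia in one subject each at 10 µg and 30 µg, 6–8 days after the boost.

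Elsewhere the SAP works dose by dose: separate safety sets for prime and boost (Section 6), AE onset counted from the corresponding immunization (7.1.2), and TEAEs summarised after each immunization (7.6.1). Vital signs and laboratory values do not follow that pattern.

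**Working it through.** **1. Pre-injection laboratory draw, source by source**

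| Source | Visit 1, before prime | Visit 5, before boost |
|---|---|---|
| 9.3.2 item 6 | listed | listed |
| 9.1.6 | not listed | not listed |
| Synopsis | not listed | not listed |
| Table 2, both age groups | not marked | not marked |

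**2. Do the blood-volume tables leave room for it?** The stated totals reproduce from the stated visit totals (mL):

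- Adults: 18 + 48 + 15 + 10 + 18 + 63 + 48 + 15 + 51 + 15 = 301.
- Elderly: 18 + 48 + 15 + 10 + 18 + 63 + 15 + 18 + 15 = 220.
- Visit 5, both groups: pregnancy 3 + IgG 7.5 + neutralizing antibody 7.5 = 18, exactly as stated. No laboratory blood is budgeted.
- Visit 1, both groups: visible rows 7.5 + 7.5 + 25 = 40 against 48 stated. The same 8 mL difference appears at every visit with a cell-mediated immunity sample (adult Visits 1, 6, 8 and 11; elderly Visits 1 and 6) and nowhere else. Adult Visit 8 has no safety laboratory, so the difference fits a removed row and not a hidden laboratory draw. It is not an error in the plan.

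**3. Totals if the 9.3.2 draws are intended.** Volumes per test are in Section 9.1.6.4. The panel is an assumption.

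- Haematology, chemistry and ferritin: 2 + 4 + 4 = 10 mL.
- With thyroid and coagulation: 10 + 3 + 2 = 15 mL.

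| | Stated | Both visits | Visit 5 only |
|---|---|---|---|
| Adults | 301 | 301 + 20 = 321 to 301 + 30 = 331 | 311 to 316 |
| Elderly | 220 | 220 + 20 = 240 to 220 + 30 = 250 | 230 to 235 |

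**4. Age of the reference value**

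- Vital signs: baseline on Day 1, boost on Day 22, so 22 − 1 = 21 days (19 to 23 with the ±2-day window). The unused Visit 5 reading is from the same day.
- Haematology and chemistry: the last scheduled value before the boost is Visit 3 (Day 8), 22 − 8 = 14 days earlier. With windows this runs from 20 − 9 = 11 to 24 − 7 = 17 days. Visit 6 follows the boost by 29 − 22 = 7 days.
- Thyroid and coagulation: the only scheduled value between prime and boost is at 24 h after the prime.
- Screening laboratory to Visit 6: 29 − (−14) = 43 days if the Day −14 column header is used. It is about 29 − (−6) = 35 days if the 7-day limits in Table 2 footnote k and Section 9.1.6.3 govern. The documents do not settle which applies.

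**The case against.** A reader might infer that boost effects have no pre-boost reference at all. The documents do not support that. Vital signs are read before the boost at Visit 5, and haematology and chemistry are taken on Day 8. SAP 7.6.2 and 7.6.3 summarise values at each time point, so these appear in the tables. The randomized placebo group gives a concurrent comparison at Visit 6, although it estimates the effect of both doses together. What remains is that within-subject change across the boost is not reported.

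The secondary laboratory endpoint is the proportion of subjects with abnormal markers at stated times, not change from baseline, and most grading limits are absolute. Adding a change column leaves that endpoint as it is. The exceptions are the haemoglobin-change rows of Appendix C Table 4, where the grade itself depends on the baseline.

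It can be said that Table 2 governs, and that the lists in 9.3 are loose menus. Section 9.3.5 likewise lists laboratory blood for post-vaccination visits generally, although several have no draw. This makes the mismatch less likely to mislead but does not remove it. A reader might also infer that different sites would produce different baselines. SAP 4.1 names one implementing institution, so that does not follow.

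The single baseline is pre-specified and identical in protocol and SAP, and protocol Section 13.1.6 also takes vital-sign change from it. Section 13.1.4, with its per-immunization principle, sits under the primary endpoints and chiefly concerns AEs and solicited reactions. In a descriptive Phase I study without formal testing, a second reference is therefore an improvement and not the correction of an error. That stands.

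Finally, a Day 8 laboratory reference is weak. Section 4.2.4.1 has lymphocyte counts returning to normal 6–8 days after vaccination, so Day 8 may still reflect the prime dose.

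**Conclusion.** Two findings stand. Section 9.3.2 item 6 conflicts with Table 2, the blood-volume tables, the synopsis and 9.1.6 at both vaccination visits. The consequence for blood volume is conditional: 20–30 mL per subject if the draws are meant at both visits, 10–15 mL if at Visit 5 only, and nothing if they are not meant. Which schedule applies is for the sponsor to decide.

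The SAP also leaves unused, as a reference, a same-day pre-boost vital-sign reading and measures acute post-boost change from about 21 days earlier. Using that reading is a better method at almost no cost. No gain in precision can be quantified, because the documents give no correlation between readings. No planned test or decision rule depends on this, and the defined laboratory endpoint is unaffected. It is a worthwhile, inexpensive improvement and does not threaten the trial's conclusions.

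**What to change.** 1. **Protocol.** Reconcile 9.3.2 item 6 with Table 2, the two blood-volume tables, the synopsis and 9.1.6. If the draws are intended, name the panel and restate the 301 mL and 220 mL totals.
2. **SAP 7.1.2 and 7.6.3.** Define a dose-specific reference. Report the 1, 3 and 6 h post-boost vital signs also as change from the Visit 5 pre-boost reading, and keep the tables against the pre-prime baseline.
3. **SAP 7.6.2.** For Visit 6 laboratory values, also report change from the last pre-boost value. That is Visit 5 if a sample is drawn there; otherwise Visit 3 for haematology and chemistry, as a supplementary display with a note that Day 8 may still reflect the prime dose.

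The cost is one protocol clarification, a few SAP sentences and extra columns in existing tables. The vital-sign and Visit 3 references need no new data.
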